### Sample size

The aim of this research is to determine that FCP is not substantially worse (non-inferiority analysis) than GP based practice. For the purpose of assay sensitivity, the study is designed as a three arm design which includes usual GP care, FCP and FCPAQ. This sample size computation also accounts for the similarities of patients within each GP centre and treats each GP centre as a cluster within which patients are nested.

Based on Bishop et al (36) a non-inferiority margin of 2 units in SF-36 scale, that is the standard practice is either superior or worse no more than by 2 unit is assumed. Previous research in MSKD, such as Angst et al. (45) has estimated a minimal clinically important difference from 4 points for the SF-36v.2 PCS subscale. The standard deviation of the difference between the SF-36 score between models are assumed to be 6.5 based on Salisbury et al (7). In a one sided 0.05 significance non inferior hypothesis test, to achieve 80% power, 132 subjects are required. To account for the hierarchical nature of the design, i.e. patients are nested within GP centres, this number should be inflated by the design effect.

The design effect for a cluster size of 14 and an intra cluster correlation coefficient (ICC) of 0.0075 (29) will be 1.09, requiring a total sample size to 145 per arm. After allowing for attrition of 20%, the total subjects required per arm is increased up to 181, making the total of at least 13 GP centres per arm, and a per practice sample size of approximately n=14.

It is suggested to randomise 13 GP centres to each physio model and recruit 14 patients with MSKD within each GP centre. In our pilot study, 814 patients consulted with MSKD over 6 months (practice population ~6200). Similar studies in primary care (7, 36) report estimates of 40% of consulting patients being eligible and consenting, we are confident in recruiting the required sample, enabling comparisons between sites and models.

In the analysis, GP centres are included as a random effects in a General Linear Mixed model to account for similarity of patients within each GP centre. The sample size computation was performed using a combination of nQuery 8 and SAS version 9.4 software.

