By definition, GPs have an extensive knowledge of the initial and ongoing management of multiple conditions. However, evidence suggests there is considerable variability in GP treatment of MSKDs, with care being offered that is inconsistent with national guidelines, and an under use of cost-effective strategies (such as exercise and self-management) (29). Furthermore, data suggest that many referrals to secondary care orthopaedic and scanning services may be inappropriate, resulting in increased waiting times and the potential for delay in cases that do necessitate urgent attention (14). There is a growing belief that GPs may not be the most appropriate healthcare professionals to manage the MSKD population, given their limited specialist musculoskeletal training (8, 30). By contrast, there is emerging evidence that physiotherapist practitioners expert in MSKDs are effective in making diagnoses and in achieving successful clinical outcomes; demonstrate good levels of patient satisfaction; and save money on unnecessary referrals (31-32). However, given the complexity of patients who may present with MSKD alongside multi-morbidities, it is as yet unclear whether non-physician led assessment and examination may lead to sub-optimal management. To date there is no systematic review specific to this emerging model of FCP and much of the available evidence is based on single case report and local audit data. This is reflected in 'The future of primary care. Creating teams for tomorrow' report (33), which recommends further research in this area.

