### 3. Why this research is needed now

An emerging model and workforce development is First Contact Physiotherapy (FCP), a rapidly developing approach to managing MSKD in primary care (15), whereby a specialist MSK physiotherapist located within general practice undertakes the first patient assessment, diagnosis and management without the requirement for prior GP consultation. Furthermore, the expanding competency framework within physiotherapy means that in addition to the traditional skills of assessment, exercise provision, education and manual therapy, some FCPs can be accredited to prescribe medication, order scans, inject joints and list for surgery (15). Whilst FCP continues to expand across the UK, and is gaining significant commissioning momentum, there is at present limited evidence on the effectiveness of this approach and the context within which it is applied; local audits suggest this model produces potential cost savings and service benefits. Pilot schemes throughout the UK indicate freeing up of GP appointments; reduction in secondary care referrals; fewer scan requests; increased patient satisfaction; and potential cost-savings of approximately £1000 per week per GP surgery (26). Moreover, there is institutional support for the role from the Royal College of General Practitioners, Chartered Society of Physiotherapy and commissioning groups across the UK (27). However, current observations from service audits and a single case study carried out by the applicants suggest that local context (e.g. time to appointment, service publicity, patient awareness, receptionist triage, ease of access to other NHS services, patient demographics) is relevant to the effectiveness, and acceptability of the model.

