#### 5.3 Work Package 3 - Realist evaluation

#### Study design

Mixed methods case study Realist Evaluation of FCP in primary care. To assess the clinical and costeffectiveness of FCP service delivery models and non-FCP physiotherapy provision, we will recruit patients within GP practices who are actively undergoing physiotherapy management for a current MSKD and collect longitudinal data over a 6 month period. Each case study will also combine qualitative interviews with key stakeholders guided by pre-determined programme theories.

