### Case study sampling and recruitment

Sampling: We require 39 case study sites across the UK, representing key sampling criteria (e.g. geographical location) that are likely to impact on service delivery. Case study sites will be sub-categorised into three strands:

- i. FCP (n=13)
- ii. FCP has additional qualifications [FCPAQ] (i.e. non-medical prescribing, injecting) (n=13)
- iii. No FCP service is available, physiotherapy provision via a different pathway [PT] (n=13)

In order to achieve a wide geographical sample, case study sites will be selected from England, Wales, Scotland and Northern Ireland. Amongst these, we will also ensure a range of urban and rural environments are included, and a range of sample deprivation based on GP population postcode deprivation index.

We will also record the duration that the service has been established as embeddedness is likely to impact on service outcomes. These will not be selection criteria for the sampling matrix, but the impact of service duration will be explored qualitatively.

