#### **Inclusion Criteria**

- (i) Patients consulting with a suspected MSKD episode, defined as any acute or chronic disorder related to the spinal or peripheral musculoskeletal system;
- (ii) Not consulted for the same problem in preceding 3 months;
- (iii) 18 years and over;

(iv) Willing to provide informed consent for healthcare records to be viewed by specified members of the research team for the purpose of this study.

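### The three-arm design is said to provide assay sensitivity, but no arm is a reference with an established difference on the SF-36 PCS, so the design lacks that property (minor)

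*Protocol*

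**What the plan says.** Under Sample size (Work Package 3), the protocol gives the purpose of the comparison: "The aim of this research is to determine that FCP is not substantially worse (non-inferiority analysis) than GP based practice". The next sentence gives the reason for having three arms: "For the purpose of assay sensitivity, the study is designed as a three arm design which includes usual GP care, FCP and FCPAQ".

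The arms are described in the same work package. Under Case study sampling and recruitment, two strands are FCP and FCP with additional qualifications (FCPAQ, meaning prescribing and injecting). The third is: "No FCP service is available, physiotherapy provision via a different pathway [PT] (n=13". The Study design paragraph says the study will recruit "patients within GP practices who are actively undergoing physiotherapy management for a current MSKD".

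On prior evidence, section 3 says of FCP that "there is at present limited evidence on the effectiveness of this approach and the context within which it is applied". Section 2 says of the comparator that "there is considerable variability in GP treatment of MSKDs".

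The Data analysis section compares PCS change across the three models by one-way analysis of variance, with pairwise t-tests if that is significant. Regression and a mixed model with site as a random effect follow.

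**The concern.** Assay sensitivity is a study's ability to detect a difference between treatments when one exists. It matters most in a non-inferiority study, because a finding of similarity has more than one explanation: the treatments may all work, none may add anything, or the study may be unable to tell them apart. The usual design remedy is a further arm, such as placebo, no treatment or a reference of known effect, whose difference from the comparator is established in advance.

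FCPAQ is not such an arm. It is a second version of the service being evaluated. The sentence therefore tells the reader that the ambiguity of a similar result has been dealt with by design, when it has not.

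What is at stake is how a non-inferior result is read. Section 4 sets out to establish the clinical effectiveness of common FCP models. Research question (c) in section 4.3 asks whether patients gain meaningfully from FCP, and the results are to feed a commissioning pack. A reader who trusts the assay-sensitivity clause could take non-inferiority alone as the answer to that question.

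**Working it through.** **1. Does any arm have a known difference from another on the primary outcome?** Taking the arms in turn:

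- *Usual GP care* is the comparator. Physiotherapy remains available through another pathway, so it is active care and not a no-treatment or minimal-care reference. Section 2 describes GP management as variable, and mentions "care being offered that is inconsistent with national guidelines, and an under use of cost-effective strategies". It gives no PCS effect for usual care over anything else.
- *FCP* is the model whose non-inferiority is to be tested. Section 3 calls the evidence on its effectiveness limited.
- *FCPAQ* is FCP with prescribing and injecting. No effect relative to FCP or to GP care is given.

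Section 1 cites local audits that favour FCP, but these concern GP appointments, investigations, satisfaction and cost. Section 2 mentions emerging evidence of good clinical outcomes with expert physiotherapists, without a PCS difference from GP care. Neither establishes a difference that this study could be expected to reproduce.

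**2. Is a reference difference built into the sample size?** The plan's own figures come from one pairwise non-inferiority calculation. Inputs from the Sample size section: margin 2, SD 6.5, one-sided 0.05, power 80%, cluster size 14, ICC 0.0075, attrition 20%. The true difference is taken as 0, which reproduces the stated figure.

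- n per arm = 2 × [6.5 × (1.645 + 0.842) / 2]² = 130.6, so 131 by the normal approximation. With the noncentral t distribution, 132 per arm is the first size to reach 80% (power 0.802). Stated: 132.
- Design effect = 1 + (14 − 1) × 0.0075 = 1.0975. Stated: 1.09.
- 132 × 1.0975 = 144.9, so 145. Stated: 145.
- 145 / (1 − 0.20) = 181.25. Stated: 181. Thirteen practices of 14 give 182.

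The figures reproduce. None of them uses an expected difference between a reference arm and the other two, so no assay-sensitivity comparison has been sized. The margin is cited to a pilot trial, with no stated effect of usual GP care over no care.

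**3. Does the analysis use a third arm as a check?** The analysis of variance and the pairwise t-tests treat the three models alike. No step requires a particular contrast to be shown before a non-inferiority result is accepted.

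**4. Result.** No arm with a known difference is described, no comparison is sized for the purpose, and no analysis step serves it. The clause names a property that the design does not have. A statistical analysis plan could add an analysis step, but it could not supply the missing reference arm.

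**The case against.** The strongest reply is that nothing depends on the phrase. Deleting it leaves every arm, sample size, endpoint and test unchanged. The aim is already worded relative to GP care, and the Outcome Measures section speaks of relative effectiveness. For a commissioner choosing between services, not worse than existing care is a usable answer. All of this stands, and it is why the point is minor. It does not make the clause true.

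A second reply is that an observed difference between any two arms would itself show that the study can detect one. That also stands. The gap concerns only a non-inferior or no-difference result.

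Three stronger readings are tempting, and the documents do not support them:

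- *Natural recovery makes the models indistinguishable.* A reader might infer this from the broad entry criterion, "defined as any acute or chronic disorder related to the spinal or peripheral musculoskeletal system". The protocol gives no recovery rate, and section 2 points the other way, noting that many patients consult repeatedly because their problem has not resolved. Any calculation of how recovery dilutes a difference would rest on an assumed fraction. It would also describe subgroup dilution, which would occur even with a placebo arm. If the overall deficit were within the 2-unit margin, declaring non-inferiority would be correct by the protocol's own criterion.
- *GP care is often poor.* Section 2 reports variability and some guideline-inconsistent care. It gives no frequency.
- *An analysis restricted to chronic disorders would repair the gap.* It would still compare three active-care arms, so it adds no assay sensitivity. Acute or chronic status is not listed among the data to be collected, and the estimate would be less precise than the overall one.

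**Conclusion.** The concern holds as a minor point of design description. The protocol attributes assay sensitivity to a three-arm design in which every arm is active care, no pair has an established PCS difference, and no analysis step uses a third arm as a check. A non-inferior or no-difference result would not show by itself that any model is effective.

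There is no numerical effect to report: the stated sample sizes reproduce and do not rest on the clause. The conclusion rests on the protocol's own description of the arms and of the prior evidence. It would change only if prior data establishing a PCS difference between two of the arms were produced.

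A reader might go further and infer that the comparison is uninterpretable, or that a no-treatment arm is needed. Neither follows. The relative comparison with usual GP care remains valid in principle, and the protocol's purpose is to evaluate services. Whether the planned analysis of variance tests the non-inferiority hypothesis at all is a separate question and is not part of this point.

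**What to change.** - In the Sample size section, delete the opening clause about assay sensitivity. Say instead that the study compares two service models under evaluation, FCP and FCPAQ, with usual GP care.
- Add one sentence saying that a non-inferior result means only that the model is not worse, within the margin, than usual GP care as delivered in the participating practices. It should add that this result will not be used alone to answer research question (c) in section 4.3.

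The cost is two sentences. No patients, sites, data items or analyses are added. The only loss is a more modest claim.

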### Recruitment

In a previous work-package (WP1) we compiled a database of FCP practice sites who have expressed an interest in participating in this stage of the research. We will categorise these respondents according to the sampling criteria presented above, and using an off-site random allocation service will randomly select sites to approach. When there is only one matched case study site to the sampling criteria, we will approach that site only. We are confident that we can recruit sufficient sites from our survey return but will also approach the NIHR local Clinical Research Network (CRN) for support in recruitment of sites as required.

Thirteen case study sites that do not provide FCP services (PT) are also required; these sites will be recruited through the CRN according to the previously described criteria.

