### Recruitment

[figure not shown]
All patients attending their GP practice consulting with an MSKD and meeting the study criteria will be eligible to participate.

In practices with FCP, all new patients consulting the physiotherapist will be provided with a participant information pack by their treating physiotherapist. This pack will include an information sheet explaining the study, contact details of the study team and a consent form with return envelope. Potential participants who require further information will be encouraged to contact the study team to discuss participation. If eligible and willing to participate, they will be required to return the signed consent form to the study team. On receipt of this form, we will contact the potential participant to confirm eligibility, and if eligible will complete the health economics questionnaire (CSRI) over the phone. We will then send a set of outcome measures with a return envelope for completion by the participant. At the participants request we can also provide the outcome measures via email for electronic completion. We will track the number of packs distributed and collect basic anonymised demographic data for all approached patients, enabling us to calculate recruitment rates and report the profile of non-participants. At the end of the data collection period we will also work with database managers in FCP practices to determine the amount of patients who continued to consult their GP for MSKD rather than the FCP, so we can present a descriptive analysis of service engagement. See figure 1.

When the patient consults, the physiotherapist also has the option to provide a recruitment pack and ask whether the patient would like a member of the study team to contact them to explain the study further. For those who would like that, the patient verbally consents to their name and telephone number only being passed to the study team. This will be managed from .nhs to .nhs secure email. The telephone call will simply include further detailing of the study after which the patient can determine whether they would like to participate.

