The analysis of the individual patient level data will be reported as a cost-effectiveness analysis using the primary outcome, SF-36 PCS, and will also be presented as a cost utility analysis, using the data collected from the EQ-5D-5L for the elicitation of the required QALY information. Details on how costs and outcomes will be gathered and the economic analysis plan, are given above. Adjustments will have to be made for any baseline variations in patient characteristics, if these are identified during the analysis. Differences in accrued QALYs between the groups will always be estimated whilst controlling for differences in baseline EQ-5D scores. The structure and type of regression model employed will be determined by the data collected and available for analysis. Given the multi-level analysis being undertaken within this study, as detailed within the statistical plan, any differences identified between any of the service models with regard to costs and/or health outcomes will be explored by an appropriate regression analysis. The base case economic analysis will adopt a direct NHS resource use cost perspective. The sensitivity analysis will explore whether or not a broadening of the analysis to a more societal perspective through the inclusion of patient out-of-pocket expenditures and productivity effects has any impact the economic conclusions.

A cost-consequences analysis will also be conducted to enable the full range of outcomes and costs, and how these are distributed across stakeholders, to be taken into consideration.

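### The protocol says GP centres are randomised to models, but sites are selected by the service they already run, so the unadjusted primary comparison is open to confounding

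*Protocol*

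**What the plan says.** **Allocation.** Under Sample size in section 5.3 (Work Package 3), the protocol states: "It is suggested to randomise 13 GP centres to each physio model and recruit 14 patients with MSKD within each GP centre".

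**How the arms are formed.** Under Case study sampling and recruitment: "Case study sites will be sub-categorised into three strands". The strands are FCP, FCP with additional qualifications (FCPAQ), and practices with no FCP service, 13 sites each. For FCP sites the Recruitment text says "we compiled a database of FCP practice sites who have expressed an interest in participating in this stage of the research", and that the team, "using an off-site random allocation service will randomly select sites to approach". Where only one site matches the criteria, that site alone is approached. For sites without FCP, "these sites will be recruited through the CRN according to the previously described criteria".

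**How patients enter.** In FCP practices, "all new patients consulting the physiotherapist will be provided with a participant information pack by their treating physiotherapist". In practices without FCP, GPs or reception staff hand out the packs, as each practice prefers.

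**Analysis.** Under Data analysis, the primary outcome paragraph compares change in SF-36 PCS at 3 and 6 months by one-way ANOVA, followed by unpaired t-tests to decide which model is superior. It then plans further model comparisons by stepwise linear regression on demographic and clinical features including baseline PCS, with optional site dummies and a mixed model with site as random effect. The Sample size section says the analysis uses a mixed model with GP centre as random effect.

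**Economic analysis.** "Adjustments will have to be made for any baseline variations in patient characteristics, if these are identified during the analysis". The text adds that QALY differences are always controlled for baseline EQ-5D.

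**The concern.** Randomising practices to models would make the arms comparable in expectation, and an unadjusted contrast would then be unbiased. Here the model is a feature of the practice before the study starts. Practices that have taken on FCP may differ from those that have not in deprivation, rurality, list size or case mix. They also reach the study by another route: FCP sites volunteered through a survey, while non-FCP sites come through the research network.

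The patients can differ too. FCP sites enrol people who saw the physiotherapist, and comparison sites enrol people consulting with an MSKD through the GP or front desk. Case mix could therefore differ even between similar practices.

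The protocol expects this. Section 3 says local context, including patient demographics, bears on how effective the model is, and Data analysis plans to look for inequalities between the groups. Yet the comparison that names the superior model takes no account of them. The results are meant to inform commissioning, so a biased primary contrast would matter.

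**Working it through.** **1. Is anything allocated at random?** The passages, side by side:

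- Sample size: centres are randomised to models.
- Case study sampling: the strand follows from the existing service.
- Recruitment, FCP sites: the random step chooses which interested, matching sites to approach, and lapses when only one site matches. This is random sampling, not assignment of a model.
- Recruitment, non-FCP sites: a different source, with no random step described.

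No step assigns a model to a practice, so the Sample size sentence contradicts the design.

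**2. Does the primary analysis compensate?** The ANOVA and t-tests contain no covariates and no site term. A change score uses the baseline value, but it does not remove differences in change that depend on baseline, nor differences between practices. The regression could address part of this, but it comes second and stepwise selection lets the data decide which confounders stay. A random site effect deals with similarity within centres; it does not remove confounding between arms.

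**3. The plan's sample size, reproduced.** Inputs from Sample size: margin 2, SD 6.5, one-sided 0.05, power 80%, cluster size 14, ICC 0.0075, attrition 20%.

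- n per arm = 2 × (1.645 + 0.842)² × 6.5² / 2² = 131; the t-based calculation gives 132, as stated.
- Design effect = 1 + 13 × 0.0075 = 1.0975 (stated 1.09); 132 × 1.0975 = 144.9, that is 145.
- 145 / 0.8 = 181.25 (stated 181); 181 / 14 = 12.9, that is 13 centres.

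These figures are not in dispute.

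**4. What a given bias would do (illustration).** The documents give no size for any bias, so b is assumed over 0 to 2 PCS points. SE of a pairwise difference = 6.5 × √(2/132) = 0.80.

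- False non-inferiority when FCP is truly 2 points worse and bias favours FCP: Φ(b/0.80 − 1.645)
- Power for non-inferiority at true equality when bias goes against FCP: Φ((2 − b)/0.80 − 1.645)
- A single two-sided 5% t-test finding a difference at true equality: Φ(b/0.80 − 1.96) + Φ(−b/0.80 − 1.96)

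| Assumed bias b | False non-inferiority | Power, bias against FCP | False difference, t-test |
|---|---|---|---|
| 0 | 5% | 80% | 5% |
| 0.5 | 15% | 59% | 10% |
| 1 | 35% | 35% | 24% |
| 1.5 | 59% | 15% | 47% |
| 2 | 80% | 5% | 71% |

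One way such a bias could arise, again by assumption: arms differ at baseline by 1 to 3 PCS points, and change falls by 0.2 to 0.5 points per baseline point. The bias is then 1 × 0.2 = 0.2 up to 3 × 0.5 = 1.5 points, or 10% to 75% of the margin, before any practice-level confounding. A larger sample does not reduce it.

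**5. Clustering, for scale.** In a simulation with 13 sites of 11 completers per arm and ICC 0.0075, a plain ANOVA at the 5% level rejects about 6% of the time. At the plan's ICC, confounding is the larger worry.

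**The case against.** Four points on the other side have force.

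- **Adjustment is planned.** The primary outcome paragraph itself includes baseline PCS, demographic and clinical features and a mixed model. A reader might infer from the ANOVA that the protocol plans no adjustment; that would be wrong. What stands is the ranking and the method: the adjusted analysis comes second, uses stepwise selection, and sits uneasily with the Sample size section, which presents the mixed model as the analysis.
- **The study is not presented as a randomised trial overall.** It is described as a realist evaluation with case studies, cohort data and purposive sampling. A reader might infer that an observational difference is being passed off as a randomised one. One tentatively worded sentence does not support that; it is a wording error to correct.
- **Sampling covers some practice differences.** A range of deprivation, urban and rural settings and nations is sought, and non-FCP sites are to meet the same criteria. This helps but does not guarantee balance, and it does nothing about the different patient routes.
- **The economic analysis is not left unadjusted.** Control for baseline EQ-5D is unconditional for QALYs. Only adjustment for other patient characteristics waits on an imbalance being found.

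An exact covariate list may also properly be left to an SAP. The ranking of the analyses and the use of stepwise selection are fixed in this protocol.

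**Conclusion.** The point holds. The randomisation sentence contradicts the site selection text, and the primary comparison is non-randomised with its unadjusted form placed first. It is open to confounding. One cannot go further and say that it is confounded, because the documents give neither the size nor the direction of any imbalance.

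The figures of about 35% (false non-inferiority with a 1-point bias favouring FCP; power with the same bias against it) rest on that assumed bias and on the plan's margin, SD and 132 per arm. They show how sensitive a 2-point margin is to modest bias and do not estimate the bias in this study. The contradiction and the weak protection of the primary conclusion are established from the text alone and should be corrected before analysis.

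**What to change.** 1. **Sample size:** replace the randomisation wording with a statement that practices are selected by existing service model and are not allocated to one.
2. **Primary outcome analysis:** make the primary analysis a linear mixed model with site as random effect, adjusted for baseline PCS and a confounder set fixed before analysis and kept whatever the observed imbalance. Use the patient demographic and clinical features already collected, plus the site-sampling variables deprivation, urban/rural and nation. Drop stepwise selection. The protocol does not show that acute or chronic status and body region are recorded; if wanted as covariates, their collection must first be confirmed.
3. **Decision rule:** judge the adjusted difference and its confidence limit against the 2-unit margin. Keep the ANOVA and t-tests as descriptive.
4. **Economic analysis:** apply the same pre-specified patient covariates to costs and QALYs, in addition to baseline EQ-5D for QALYs.
5. **Reporting:** describe results as adjusted associations from a non-randomised comparison.

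**Cost:** wording and a few degrees of freedom, felt mainly at practice level. With 39 sites, a linear deprivation term (1), urban/rural (1) and four nations (3) use 5, and the service model uses 2, leaving 39 − 1 − 2 − 5 = 31. Residual confounding remains after adjustment and should be stated as a limitation.
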